8.2.10 Time to Administration of First Dose of Rescue Medication

Time to first administration of rescue medication is the date/time of the earliest rescue medication use minus the date/time of T_0 . If the subject receives no rescue medication, then the value will be censored at 8 hours.

This will be analyzed using Kaplan-Meier curves for each dose level of DFN-15 to placebo with

the log-rank test. Estimated percentiles for time to first use of rescue will be tabulated by

Statistical Analysis Plan Version: 2.0

Effective Date: 08OCT2018

treatment group along with the number and percent of subjects censored.

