## 1. INTRODUCTION

[name], Limited is developing DFN-15, a new formulation of celecoxib [p-[5-p-Tolyl-3-(Trifluoromethyl) pyrazol-1-yl] benzene sulfonamide] for the indications of: (1) acute treatment of migraine with or without aura, and (2) management of acute pain in adults. This study is designed to evaluate the efficacy, safety, tolerability and pharmacokinetic properties of dosing with three doses of DFN-15 (celecoxib; 62.5 mg, 125 mg, and 250 mg) in a postoperative pain population. A single-dose, dose ranging design using the oral surgery model will be used to provide useful data in terms of analgesic onset, single-dose duration of analgesia, and effect size of pain-time curves during an 8-hour evaluation period of postoperative pain. Plasma concentrations and calculated Pharmacokinetic parameters will be used to determine the concentration-effect relationships for efficacy and safety. Efficacy assessments will attempt to identify the time to onset of analgesia, the duration of analgesia, and magnitude of analgesic effect in comparison with placebo.

NSAIDs produce meaningful analgesia without opioid associated side effects such as sedation, nausea and vomiting and they have a low risk of abuse and dependence. NSAIDs, such as celecoxib, that selectively inhibit cyclooxygenase 2 (COX-2) target the prostaglandins (synthesized via COX-2) responsible for inflammation and pain while sparing the prostaglandins responsible for maintenance and protection of the gastrointestinal (GI) tract (synthesized involving COX-1). The analgesic efficacy of COX-2 selective NSAIDs is similar to nonselective NSAIDs but celecoxib has reduced incidence of upper GI ulcers and bleeds and less GI upset. Data suggests that selective COX-2 inhibitors may be safer in the immediate pre- and peri-operative periods, especially with respect to the incidences of bleeding, incisional wound hematomas, gastro-intestinal ulceration, and they may not impact bone fusion and wound healing.

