#### **4.4. Discontinuation of Subjects**

##### **4.4.1. Procedures for Withdrawal**

A subject may request to be withdrawn from study participation at any time, without disclosing the reason if chosen not to. Subject may be discontinued from the study by the Investigator or the Sponsor at any time if either determines that it is not in the Subject’s best interest to continue participation or due to non-compliance with the protocol. Investigator is encouraged to contact the study Medical Monitor to discuss details surrounding non-compliance. Subjects who withdraw consent to continue treatment or who are discontinued from the study before completing the protocol-specified duration of treatment should be encouraged to complete the early termination assessments and procedures outlined for 8 hours after treatment initiation. Subjects will be encouraged to agree to return to the study site 7 days ( $\pm 3$  days) post-surgery for evaluation of their safety and well-being. The date the subject is withdrawn and the primary reason for discontinuation will be recorded in the subject’s case report form (CRF).

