### **8.3. General Considerations for Statistical Analysis**

#### **8.3.1. Analysis Datasets**

Modified Intent-to-Treat (mITT) Analysis Set: The mITT set will include all subjects who receive study drug, and have recorded at least one post dosing efficacy score.

Safety Set: The safety set will include all treated subjects and will be used for safety and tolerability assessments.

Pharmacokinetic Set: The pharmacokinetic set will include all subjects who have received a dose of DFN-15 and have at least one quantifiable concentration of celecoxib in plasma.

Non-compartmental analysis as specified in a PK Analysis Plan will be used to estimate pharmacokinetic parameters and to present descriptive statistics using the Pharmacokinetic Set. Additional exposure-response analysis may be built in the full statistical analysis plan (SAP). Comparisons will be performed at the 0.05 two-sided significance level unless otherwise specified. No adjustments for multiplicity will be performed. Additional details of the analysis will be provided in the SAP and/or the clinical study report. The SAP will supersede the protocol in case of a discrepancy.

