##### **8.5.3. Time to Event End Points**

There are 2 types of time to event endpoints in this study:

- 1) Time to perceptible pain relief and time to meaningful pain relief as measured by two stopwatch technique post first dose of study drug
- 2) Time to first dose of rescue medication post study drug dose

Time to event endpoints will be derived for each subject. Subjects without the event will be censored at time of last evaluation. Time to analgesic onset and time to rescue will be summarized graphically with Kaplan-Meier curves and compared across treatments using the log-rank test. Estimated percentiles for time to relief will be tabulated by treatment group along with number and percent subjects censored for this analysis. If center effect is significant based on the time weighted SPID6, the log-rank test for time to pain relief will be stratified by analysis center.

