A subject may request to be withdrawn from study participation at any time, without disclosing the reason if chosen not to. Subject may be discontinued from the study by the Investigator or the Sponsor at any time if either determines that it is not in the subject's best interest to continue participation or due to non-compliance with the protocol. Investigator is encouraged to contact the study Medical Monitor to discuss details surrounding non-compliance. Subjects who withdraw consent to continue treatment or who are discontinued from the study before completing the protocol-specified duration of treatment should be encouraged to complete the early termination assessments and procedures outlined for 8 hours after treatment initiation. Subjects will be encouraged to agree to return to the study site 7 days (±3 days) post-surgery for evaluation of their safety and well-being. The date the subject is withdrawn and the primary reason for discontinuation will be recorded in the subject's case report form (CRF).

The protocol-defined visits are presented in the following (example) table:

Table 1 Protocol-Specified Visits and Visit Windows

Study Phase	Visit Time
Screening	From days -28 to -1
Day 1 Prior to Dose	Day 1 up to 6 hours post-surgery
Day 1 Post-Dose	Day 1. Assessments at 0.25, 0.5, 0.75, 1, 1.5, 2, 2.5, 3, 4, 5, 6, 7, and 8 hours after administration of study medication
Follow-up	Day 7

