8.0 Efficacy Evaluation

8.1 Overview of Analysis Issues

8.1.1 Handling of Dropouts or Missing/Invalid Data

Subjects with missing or invalid PI NPRS data will be imputed using the following rules.

Subjects who require rescue medication will record their pain intensity (PI) NPRS, Pain Relief (PR) and Patient Rating of Treatment Satisfactoriness scores within 5 minutes prior to first use of rescue medication. These are referred to as 'pre-rescue' PI, PR, and Patient Rating of Treatment Satisfactoriness scores, respectively. Any scheduled PI or PR assessments scheduled within 4 hours after administration of rescue medication will be replaced by the pre-rescue score in the efficacy analysis. This method of replacement is referred to as the windowed Last Observation Carried Forward (wLOCF).

After any scheduled PI/PR scores within 4 hours after rescue are appropriately replaced by the pre-rescue PI/PR scores, any other scheduled PI/PR scores that are still missing intermittently and are not within 4 hours after rescue medication will be imputed using linear interpolation between adjacent observed values.

After all intermittent missing scores are imputed, any scheduled PI/PR scores missing because the subject dropped out of the study will be imputed as follows: If the subject drops out due to adverse event (AE), the PI score will be imputed using a baseline observation carried forward (BOCF) method; if the subject drops out for other reasons, the PI/PR score will be imputed using the last observation carried forward (LOCF) method. PI data with missing baseline PI score will be excluded from the analysis.

For responder endpoints, subjects that drop out will be considered as non-responders for all assessment time points after their date/time of drop out. Similarly, if a subject receives rescue medication, then the subject will be treated as a non-responder for all subsequent timepoints.

No imputation for other efficacy or safety will be performed.

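### Time to rescue: the SAP censors every unrescued subject at 8 hours, even one who left earlier, while the protocol censors at last evaluation

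*SAP*

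**What the plan says.** SAP 8.2.10 defines time to first rescue from T0 and adds: "If the subject receives no rescue medication, then the value will be censored at 8 hours". The endpoint is analysed with Kaplan-Meier curves and a log-rank test of each dose against placebo.

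Protocol 8.5.3 lists "Time to first dose of rescue medication post study drug dose" among its time-to-event endpoints and gives a different rule: "Subjects without the event will be censored at time of last evaluation".

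On precedence, protocol 8.3.1 is explicit: "The SAP will supersede the protocol in case of a discrepancy". The 8-hour rule is therefore the operative one. SAP 13.0, the section for changes to the protocol's analyses, itemises none and refers deviations to the study report.

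Both documents allow for early departure. Protocol 4.4.1 says "A subject may request to be withdrawn from study participation at any time", and SAP 2.2 repeats it. SAP 8.1.1 has rules for dropout within the scoring period ("any scheduled PI/PR scores missing because the subject dropped out of the study will be imputed as follows"). Those rules cover pain scores and responder endpoints only, and the section then excludes imputation for other efficacy data. Nothing there changes the rescue-time rule.

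**The concern.** Someone who leaves at 1.5 hours without rescue has 1.5 hours of observed rescue-free time. The SAP rule records 8 hours and keeps that person in the risk set for the remaining 6.5 hours as though under observation.

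SAP 8.2.9 uses the same 8-hour censoring for time to perceptible and meaningful relief. There it is conservative, because relief is a favourable event and an early leaver counts as not relieved. Rescue is an unfavourable event, so the same rule gives the early leaver the best possible result. This also runs against SAP 8.1.1, which counts dropouts as non-responders and carries the baseline pain score forward after dropout for an adverse event.

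At stake are the rescue-free curve, its percentiles and the log-rank test for a key secondary endpoint. Time to rescue bears on one of the aims in the protocol introduction, to identify "the duration of analgesia, and magnitude of analgesic effect in comparison with placebo".

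**Working it through.** The plan states no dropout rate, rescue rate or formal sample-size calculation, so there is no figure of its own to reproduce. The check compares the two censoring rules on the same data.

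**Inputs from the documents.** 120 subjects randomised 1:1:1:1 (SAP 2.5 and 2.6), so 120/4 = 30 per arm. Follow-up for rescue is 8 hours. The mITT population needs only one post-dose pain score (SAP 4.1), and the first is due at 15 minutes, so early leavers are in the analysis. Tests are two-sided at 0.05 (SAP 3.0).

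**Assumed, not in the documents.** Exponential time to rescue, the true share rescue-free at 8 hours, the number and timing of leavers, and (in the simulations) withdrawal unrelated to rescue risk.

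**1. Direction.** The Kaplan-Meier estimate is the product of (1 − d/r) over rescue times, with d rescued out of r at risk. The SAP rule leaves each d unchanged and can only increase r. Every factor is then at least as large, so the curve can only rise or stay the same.

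**2. A worked arm (assumed).** Of 30 subjects, 3 leave unrescued at 1 hour, 18 are rescued between 1.5 and 7 hours, and 9 reach 8 hours without rescue.
- Last-evaluation censoring: 27 are at risk from the first rescue on, and 9/27 = 33.3% are rescue-free at 8 hours; median 5.7 h.
- SAP rule: (9 + 3)/30 = 40.0%; median 6.0 h.

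**3. Expected shift per leaver at 1.5 hours.** With true 8-hour share S and exponential times, a subject unrescued at 1.5 hours remains so to 8 hours with probability S^(6.5/8). The SAP credits 1. The gain per leaver is (1 − S^(6.5/8))/30.
- S = 25% (75% rescued): 0.25^0.8125 = 0.324, and (1 − 0.324)/30 = 2.25 points. One, two and three leavers give 27.3%, 29.5% and 31.8%. A simulation of 2,000 arms gave 27.3%, 29.4% and 31.8%, against 25.1%, 24.9% and 25.0% with censoring at 1.5 hours.
- S = 20%: (1 − 0.270)/30 = 2.4 points. S = 40%: (1 − 0.475)/30 = 1.75 points. S = 60%: (1 − 0.660)/30 = 1.1 points.

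**4. Leavers spread over 0–4 hours.** Mean upward shift at 8 hours, from 2,000 simulated arms per cell. An assigned leaver may be rescued before leaving.

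| True share rescue-free | 0 leavers | 1 | 3 | 5 |
|---|---|---|---|---|
| 20% | 0 | +1.6 | +4.9 | +8.2 |
| 40% | 0 | +1.3 | +4.1 | +6.7 |
| 60% | 0 | +1.0 | +2.8 | +4.7 |

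Last-evaluation censoring recovered the true share to within 0.3 points in every cell. At a true share of 40%, 5 leavers moved the typical median from 6.1 to 6.8 hours; 1 or 2 left it unchanged.

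**5. Log-rank test under equal hazards.** 1,500 simulated comparisons per row, 30 per arm. Negative z favours active.

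| Leavers, active / placebo | True share | Rejects, last evaluation | Rejects, SAP rule | Mean z, SAP rule |
|---|---|---|---|---|
| 2 / 2 | 20% | 4.5% | 4.4% | 0.04 |
| 2 / 2 | 40% | 4.4% | 3.9% | 0.03 |
| 3 / 0 | 20% | 3.8% | 5.1% | −0.39 |
| 3 / 0 | 40% | 4.1% | 5.6% | −0.30 |
| 5 / 0 | 20% | 4.7% | 8.6% | −0.60 |
| 5 / 0 | 40% | 5.1% | 6.7% | −0.48 |
| 0 / 3 | 20% | 4.2% | 5.5% | 0.37 |
| 0 / 3 | 40% | 4.1% | 5.3% | 0.29 |

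Equal numbers of leavers shift nothing. Unequal numbers move the test towards whichever arm has more leavers.

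**The case against.** The strongest reply is that few subjects can be affected. They are confined for at least 8 hours after dosing (protocol synopsis, Study Visits). A subject in pain may ask for rescue, and waiting two hours is only encouraged (protocol 5.15). Rescue does not end participation, and a rescued subject is an event at the actual time under either rule. Only someone who leaves both early and unrescued matters. This stands, and it also answers one tempting inference, that subjects with poor pain control will be counted as the longest responders: most of them have a reason to take rescue and stay. Departure for an adverse event, or for a reason the subject need not give, remains possible. Protocol 4.4.1 encourages those leaving to complete the 8-hour procedures, but protocol 6.5.4 has these collected at early termination, so that does not extend observation.

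Second, even three leavers in an arm of 30 move the estimate by about 7 points (3 × 2.25), less than one binomial standard error, √(0.25 × 0.75/30) ≈ 8 points. That is correct, but the shift is systematic and avoidable.

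Third, the SAP may lawfully change the protocol's rule, and the new rule agrees with SAP 8.2.11, which keeps all mITT subjects in the denominator for rescue use. Precedence is indeed settled, and since SAP 13.0 itemises no changes, its silence on this one carries little weight. Agreement with a simple proportion does not justify a follow-up time that was not observed.

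**Conclusion.** The rule is wrong as written for any subject who leaves before 8 hours without rescue. For such subjects the direction is certain: the rescue-free curve rises in each arm that has them. The size is about 2 points at 8 hours per leaver at 1.5 hours in an arm of 30, if 75% are rescued by 8 hours (1.1 to 2.4 points for true rescue-free shares of 60% to 20%). It is zero if nobody leaves.

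A reader might infer that the trial's duration of analgesia is inflated, or that DFN-15 is favoured. The documents do not support either. They give no dropout rate and nothing to suggest that leaving will differ by arm. The placebo curve would rise in the same way, and the log-rank test is biased only under unequal leaving. Nor do the documents make time to rescue the sole measure of duration; the introduction states that aim for the efficacy assessments in general. This is one of several key secondary endpoints, tested without multiplicity adjustment (SAP 8.3). SPID6 does not use the rule.

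The point is therefore a small but clear correction to a key secondary analysis.

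**What to change.** Replace the sentence in SAP 8.2.10 with: *Subjects without rescue are censored at 8 hours or at their last evaluation/withdrawal, whichever is earlier.* This restores the protocol's principle, leaves subjects observed to 8 hours as they are, and changes no result if nobody leaves early. The pain assessment required at early termination supplies a time. If the sponsor prefers to keep the 8-hour rule, SAP 13.0 should record and justify the departure from protocol 8.5.3.

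Optionally, add one sensitivity analysis that counts withdrawal before 8 hours for an adverse event or inadequate relief as an event, since such withdrawal may be informative and simple censoring cannot address that. The documents do not require it. Because reasons may be withheld, it should state in advance how undisclosed reasons are classified.

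The cost is one sentence in the SAP and, if the option is taken, one further log-rank run. No new data are needed.

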8.2.11 Proportion of Subjects Receiving Rescue Medication

The proportion of subjects receiving rescue medication uses the number of subjects receiving rescue medication at any time as the numerator and the number of subjects in the mITT population as the denominator.

Summary tables will present the by-treatment group descriptive statistics of proportions with active vs. placebo odds ratios, 95% confidence intervals and CMH chi-square and Fisher exact *p*-values. The proportion of subjects receiving their first dose of rescue at each timepoint will be presented graphically.

8.3 General Analysis Methods

SPID and TOPAR endpoints will use Dunnett's test to account for multiplicity within each of those endpoints. All other *p*-values are presented without adjustment for multiplicity. The mITT population will be primary population used for all efficacy analyses. The PP population will be used as a supplemental analysis for SPID, TOTPAR, PID by timepoint, PR by timepoint, and peak pain relief.

In all cases, the null hypothesis being tested is that the means of the two treatment groups are equal, and the alternative is that the means are not equal:

- H₀: there is no treatment difference
- H_A: there is a treatment difference

If more than 1 center is used, then center effect will be added to the SPID6 ANCOVA model to investigate the impact. If the center effect is significant at the 0.05 level, then center will be added to the log-rank test for time to meaningful and perceptible pain relief analyses. Additionally, treatment-center interactions will be tested in the ANCOVA analysis of the SPID6 endpoint. If this interaction is significant at the 0.10 level, then the interaction term will be included in a sensitivity analysis.

8.4 Exploratory Analysis

Exploratory analyses may be performed to describe other results of interest from the study. Any such analyses will either be documented in a subsequent version of this SAP or in a *post hoc* SAP.

8.5 Examination of Subgroups

The primary endpoint (SPID6) will be analyzed by subgroup for gender (male or female), qualifying pain intensity category (2=moderate or 3=severe on 4-point scale), and BMI (<30 or ≥30).

9.0 Safety Evaluation

9.1 Overview of Safety Analysis Methods

All safety outcomes will be summarized using the safety population. Safety outcomes include:

- Incidence of treatment-emergent AEs (TEAEs)
- Changes from baseline in clinical laboratory test results

- Changes from baseline in vital sign measurements
- Changes from baseline in physical examinations.
- Changes from baseline in ECG findings,
- Evaluation of surgical wound healing.

9.2 Adverse Events

Treatment-emergent AEs are defined as AEs that start or worsen in severity after the first exposure to study medication through the Day 7 visit. Verbatim terms used by investigators to identify AEs in the CRFs will be mapped to the appropriate preferred (PT) and system organ class (SOC) using a standardized coding dictionary (MedDRA Version 21.0 or higher). All coding will be reviewed prior to database lock. All recorded AEs will be listed, but only TEAEs will be summarized.

Statistical Analysis Plan Version: 2.0

Effective Date: 08OCT2018

In addition to a listing of all TEAEs, separate listings of subjects with SAEs and listings of subjects with severe, treatment related, and AEs leading to premature discontinuation will be provided.

An overall summary will be prepared giving for each treatment group, all DFN-15 groups combined and overall of both the number of events and the number of subjects with TEAEs, SAEs, TEAEs by severity, TEAEs by relationship to treatment, and TEAEs leading to premature discontinuation.

The incidence of TEAEs will be summarized for each treatment group by SOC and PT within SOC (sorted in descending order by overall frequency). These summaries will be given in separate tables for the following categories of TEAEs:

- All TEAEs
- TEAEs leading to premature discontinuation
- SAEs

Also summarized will be TEAEs by maximum severity and by maximum relatedness to treatment. Adverse events will be deemed treatment related if they were recorded as probably, possibly, or definitely related.

If a given subject experiences a TEAE that maps to the same PT more than once, the subject will be counted once for the PT at its greatest severity (i.e., mild, moderate, or severe) and causality (i.e., attribution to study medication).

Duration of an AE will be computed in days (or in hours when duration of the AE is less than 1 day) as the stop date/time of the event minus the start date/time plus 1. If reported as ongoing at the time of database lock, the stop date/time is defined as the date/time of the last visit or the last date/time of any AE for the subject in the database, whichever is later. If an AE is considered resolved, but the stop date is missing, the last day of the month will be imputed if the month and year are available. If only the year is available, and the year is the same as the year of the last visit, the stop date will be the latest of the last visit date or latest AE for the subject in the database. If the year of the AE is prior to the year of the last treatment, the end day and month will be set to 31 December.

For missing or partial start dates, it is most conservative to impute them as temporally related to the first dose of study medication. The following chart will be used to impute start date:

Statistical Analysis Plan Version: 2.0 Effective Date: 08OCT2018

Table 2 Table of Adverse Event Start/End Date/Time Imputation Rules

Missing Portion	Prior to Treatment	Same as Treatment Start Date	After Treatment Start Date
Day	Month and Year < Month and Year of first treatment:	Month and Year = Month and Year of first treatment:	Month and Year > Month and Year of First Treatment:
	Start Day = first day of the month	Start Day = Day of first treatment	Start Day = first day of the month
	Stop Day = last day of the month	Stop Day= last day of the month	Stop Day= last day of the month
Day and Month Define Day as above, then:	Year < Year of first treatment:	Year = Year of first treatment:	Year > Year of first treatment:
	Start Month = July	Start Month =	Month = January
	Stop Month = Dec	Month of first treatment	Stop Month = Dec
		Stop Month = Dec	
Day, Month, and Year	To be conservative, completely missing start dates will be set to the date of first treatment, completely missing end dates will be set to the date of last contact.		
Time	Missing start times will be imputed as 00:01 (or the start time of the first dose administration if AE occurred on the date of first dose administration)		
	Missing stop times will b	e imputed as 23:59	

After following these imputation rules, if the start date is imputed as a date after the end date, the start date will be set to the end date to provide a positive duration for the AE.

Missing assessments for AE study medication relationship, or severity will be analyzed as related, severe, and associated, respectively. No other imputation is planned for safety data unless otherwise specified below.

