#### **8.5.5. Proportion of Subjects Requiring Rescue Medication**

The analysis will evaluate the relative risk (DFN-15 vs. Placebo) of requiring rescue medication during the study. Proportions of subjects who used rescue medication at least once will be tabulated by treatment group; differences between each DFN-15 dose group and placebo will be assessed using the relative risk approach. Observed incidence, estimated relative risk ratio and corresponding 95% CI for the relative risk will be provided.

The number of times rescue medication used during the in-patient 8 hour evaluation phase will also be tabulated by treatment group. Incidence of rescue medication use will be summarized and analyzed with a generalized linear model using a logit link.

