2.0 Protocol Summary

2.1 Study Objectives

2.1.1 Safety

To evaluate the safety of DFN-15 relative to placebo control in subjects with moderate to severe acute pain following elective bilateral lower third molar extraction, as assessed by:

- Treatment emergent adverse event (TEAE) reports,
- Laboratory test results,
- Vital signs,
- Physical examinations,
- ECG findings,
- Evaluation of wound healing.

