At screening and upon admission/Check-in (Day 1) to the clinic, prior to dental surgery, subjects will be screened for alcohol consumption and illicit drug use by alcohol breathalyzer test and urine drug screen, respectively. Subjects continuing to meet I/E criteria will proceed to undergo their planned surgery for extraction of the impacted mandibular molars on both sides. As a prerequisite for randomization, subjects will be required to report within 6 h post-surgery (Baseline period): a) "moderate" to "severe" baseline pain as characterized on a 4-point categorical pain intensity (PI) scale (0= none, 1= mild, 2=moderate, 3= severe), and b) a score of ≥5, on the 11-point Numerical Pain Rating Scale (NPRS) where 0 represents 'no pain' and 10 represents 'worst pain imaginable', on the provided paper diary. Eligible subjects will be randomized and will receive a single dose of the assigned study treatment (a total volume of 10 mL). The start time of dosing will be recorded as T0. Subjects will be randomized and administered the study medication within 15 minutes of meeting the post-operative inclusion criteria (baseline score).

Subjects with inadequately controlled pain symptoms may request rescue analgesic medication. The rescue medication for this study will be 1-2 oxycodone 5 mg/acetaminophen 325 mg q 4 h PRN. Subjects will be encouraged to delay using the rescue medication if their pain is tolerable until 120 minutes post-dose of study medication. A subject who is administered rescue pain medication will continue completing pain assessments until 8 hours after treatment initiation. The use of ice packs will not be allowed in the 8-hour observation period. All randomized subjects will be provided with a paper diary to record pain assessments. A subject training program will be implemented to ensure that all subjects understand the relevant scales and assessments prior to study participation. At study medication administration, two stopwatches will be started, to measure times to 'perceptible' and 'meaningful' pain-relief. Subjects will be instructed to stop the first stopwatch when they first perceive pain relief to occur (time to perceptible relief). Subjects will be instructed to stop the second stopwatch when they first experience meaningful pain relief (time to meaningful relief). Stopwatch times of perceptible relief and meaningful relief will be recorded using exact stopwatch time displayed.

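### The treatment-emergent adverse event tables take no account of opioid rescue, so if DFN-15 reduces rescue use the comparison with placebo shifts in its favour, and no planned table shows by how much

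*SAP*

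**What the plan says.** The SAP's safety objective (2.1.1) is comparative: "To evaluate the safety of DFN-15 relative to placebo control in subjects with moderate to severe acute pain". SAP 9.2 sets the counting window: "Treatment-emergent AEs are defined as AEs that start or worsen in severity after the first exposure to study medication through the Day 7 visit". It then limits what is tabulated: "All recorded AEs will be listed, but only TEAEs will be summarized". The main table is by arm: "The incidence of TEAEs will be summarized for each treatment group by SOC and PT within SOC". Further tables give severity, relatedness, discontinuations and serious events. None of the adverse event tables in SAP 15.1 (14.3.1.1 to 14.3.1.6) or the adverse event listings in 15.3 (16.2.11.1 to 16.2.11.3) refers to rescue.

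On the rescue drug, SAP 2.2 states: "The rescue medication for this study will be 1-2 oxycodone 5 mg/acetaminophen 325 mg q 4 h PRN". It is available in all four arms. Protocol section 1 contrasts NSAIDs with opioids in these terms: "NSAIDs produce meaningful analgesia without opioid associated side effects such as sedation, nausea and vomiting".

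Rescue use is itself an outcome. Protocol 8.5.5 states: "The analysis will evaluate the relative risk (DFN-15 vs. Placebo) of requiring rescue medication during the study". SAP 8.2.10 and 8.2.11 plan time to first rescue and the proportion rescued. No expected rate is given for any arm.

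**The concern.** The SAP deals with rescue throughout the efficacy analysis. Pain scores scheduled within 4 hours after rescue are replaced, and rescued subjects become non-responders (8.1.1). Peak relief uses only scores before rescue (8.2.6), and stopwatch times are censored if rescue comes first (8.2.9). The safety analysis has no counterpart, although the same tablets can cause nausea, vomiting and sedation.

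If DFN-15 works, fewer DFN-15 subjects take the opioid and fewer have its side effects. The all-TEAE table then combines the tolerability of DFN-15 with the opioid sparing that its efficacy brings. An excess of nausea caused by DFN-15 could be offset by opioid nausea on placebo, and the planned tables would not show it. The same could happen between DFN-15 doses if lower doses lead to more rescue.

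**Working it through.** **No plan figure to reproduce.** The documents give no event rate, rescue rate or power. SAP 2.6 says the sample size had no formal calculation. Allocation is 120/4 = 30 per arm.

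**Model, for illustration only.** Let b be the risk of a TEAE without rescue, r the proportion rescued, and o the added risk of an opioid-type TEAE once rescued, with the two sources independent:

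P(TEAE) = 1 − (1 − b)(1 − r·o)

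All three inputs are assumptions. One DFN-15 rate stands for any one dose arm.

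**No true difference.** With b = 10% in both arms, DFN-15 minus placebo is −(1 − b)·o·(r_placebo − r_DFN-15) = −0.9·o·(r_placebo − r_DFN-15).

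| Rescue, placebo / DFN-15 | o = 10% | o = 20% | o = 30% |
|---|---|---|---|
| 60% / 60% | 0 | 0 | 0 |
| 60% / 40% | −1.8 | −3.6 | −5.4 |
| 80% / 50% | −2.7 | −5.4 | −8.1 |
| 90% / 40% | −4.5 | −9.0 | −13.5 |

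Values are percentage points. The non-zero range of 1.8 to 13.5 points is 0.018 × 30 = 0.5 to 0.135 × 30 = 4 subjects per arm.

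**A true DFN-15 excess of 10 points.** Take b = 20% on DFN-15 and 10% on placebo, with rescue 50% and 80%.

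- o = 20%: placebo 1 − 0.9 × 0.84 = 24.4%; DFN-15 1 − 0.8 × 0.90 = 28.0%; observed difference +3.6.
- o = 30%: placebo 1 − 0.9 × 0.76 = 31.6%; DFN-15 1 − 0.8 × 0.85 = 32.0%; observed difference +0.4.

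Most or nearly all of the excess disappears. With equal rescue of 60%, the same excess loses under 2 points.

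**Sampling error.** The approximate 95% half-width for 30 against 30 is 1.96·√(2p(1 − p)/30): 15.2 points at p = 10%, 20.2 at 20% and 23.2 at 30%. Every shift in the table is smaller than this. Sampling error can fall either way, however, while the shift always favours the arm with less rescue.

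**Can the relatedness table separate the events?** Protocol 7.5.2 lets the investigator class an event as not related when a different drug caused it, and Table 14.3.1.6 reports relatedness by arm. But the possibly related category in 7.5.2 admits an equally likely alternative cause, and SAP 9.2 counts that category as treatment related. A missing relationship is also analysed as related. A blinded investigator who sees nausea after both study drug and oxycodone may reasonably choose possibly related, and the event then enters the treatment-related count.

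**The case against.** The strongest reply is that counting every TEAE whatever rescue was taken is a proper treatment-policy summary. It describes what happened to subjects assigned to each arm with rescue available. It would be biased only for a different question, the effect of the drug without rescue, which the documents do not pose. This stands, and it is why the current tables should remain the main summary.

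A reader might infer that placebo subjects are bound to take more rescue, so that DFN-15 tolerability is certainly flattered. The documents do not support that. They give no rescue rate, and rescue use is an endpoint still to be estimated. With equal rescue and no true difference, the shift is zero.

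A reader might also infer that the all-TEAE table is the only tolerability comparison. It is not. Relatedness, severity, discontinuation and serious-event tables are planned by arm, and Tables 14.2.11 and 14.2.12 will show any imbalance in rescue. Those tables show that an imbalance exists, but not which events followed rescue. A reader would have to match listing 16.2.10.5 with listing 16.2.11.1 by hand.

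A pre-rescue table has weaknesses of its own. Rescue is a post-randomisation event driven by pain, so subjects still at risk are no longer a randomised comparison. Person-hour rates also assume a constant hazard, which is doubtful for a single dose that, by protocol section 1, peaks within one hour. Both criticisms are right, and they limit how the table may be read.

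Finally, protocol section 2 makes safety a secondary objective of this Phase 2 study, and the synopsis plans no safety testing. That keeps the point modest. But a descriptive safety reading rests directly on these counts.

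**Conclusion.** The point holds in conditional form. The TEAE tables run from dosing to Day 7 with no account of opioid rescue, while the stated safety objective is a comparison with placebo. If DFN-15 reduces rescue use, the all-TEAE comparison shifts in its favour, by roughly 2 to 13 points under the assumed ranges when there is no true difference. The direction depends on DFN-15 reducing rescue. The size depends on rescue and opioid-event rates that the documents do not give. At 30 per arm the shift is within sampling error. The relatedness table reduces the problem but does not remove it.

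The planned tables are not wrong and no efficacy conclusion is affected. What is missing is a supplementary summary that would let the comparison with placebo be interpreted.

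**What to change.** Keep every current TEAE table as the main summary. Then:

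1. In SAP 9.2 and 15.1, add one descriptive table by arm of TEAEs with onset before first rescue, up to 8 hours after dosing. Show counts, time at risk and a cumulative incidence censored at first rescue, not person-hour rates alone. The cumulative incidence avoids the constant-hazard assumption. It still treats stopping at rescue as non-informative, and the table should say so.
2. In listing 16.2.11.1, flag each event as starting before or after first rescue.
3. Flag and show separately any event whose dosing-day start time was imputed. Table 2 of the SAP sets a missing time on the dosing day to the time of dosing, and sets a wholly missing start date to the date of first treatment. Without a separate category, such events would be classed as pre-rescue by default.

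The SAP already derives time to first rescue (8.2.10) and handles event start times (9.2), so nothing new need be collected. Specifying the table now avoids the post hoc label that SAP 1.0 and 11.0 would otherwise attach.

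The cost is one table and one flag. The table will have sparse cells and shorter follow-up in arms that rescue early. Because stopping at rescue is not random, it must be read descriptively beside the all-TEAE tables.
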